5.3 WHY THE TRIAL IS NECESSARY?

This pilot study aims to assess the feasibility of randomising 60 coronary artery bypass surgery patients with impaired kidney function in 6 months within a single-centre for

intraoperative haemofiltration. This should allow us to investigate the likelihood of recruitment into the main definitive study and explore issues that may impact recruitment such as likely patient numbers, staff requirements, and barriers to recruitment, suitability and reliability of the outcome measures selected. In the financial year 2008-2009, up to 90 patients that would meet the inclusion criteria of the study were operated at our centre. We predict that it is highly probable that more than 100 patients that meet our inclusion criteria will be operated in the financial year 2010-2011 which is our target recruitment period. Specifically, the results will be useful in giving a preliminary indication of the impact the procedure has on healthcare pathways such as the intensive care and hospital stays since renal impairment is one of the major complications for patients undergoing cardiac operations.

Furthermore, the results of the pilot trial will begin to tell us whether a definitive randomised trial can address the underlying concerns about costs and benefits (i.e. value) of using intraoperative haemofiltration. Currently, the cost of an intraoperative haemofiltration is approximately £200 a patient which is only 3-4% of what it would cost to perform postoperative continuous veno-venous haemofiltration or dialysis in intensive care units (ICU)/high-dependent units (up to £5000-£6000 a patient over and above standard costs). If the pilot study can establish that the definitive trial can give clear evidence whether intraoperative haemofiltration for patients with renal impairment is effective at reducing the likelihood of postoperative haemofiltration, length of stay in ICU and hospital this will represent an important treatment strategy that could save the NHS millions of pounds every year. Thus there is potential for the main definitive study to influence clinical decision making, identify the level of care required to reduce length of stay in ICU and hospital for patients, improve overall operative outcomes and reduce treatment costs.

A definitive randomised trial will have the potential for increasing capacity by freeing more ICU beds (wherever the care is carried out) and wards consequently allowing more operations to be performed in the same amount of time. There is also a potential for a reduction in the number of cases who might otherwise go on to develop permanent renal damage/ chronic renal failure that would necessitate further long-term use of NHS resources.

6. TRIAL DESIGN

Single centre, randomised open-label clinical trial

6.1 Study Population: Patients that are undergoing coronary artery bypass graft (CABG) surgery and with known impaired kidney function indicated by an estimated glomerular filtration rate (eGFR) <60 ml/min.

6.2 Selection of Study Participants: **Renal dysfunction will be assessed preoperatively on the basis of reduced estimated glomerular filtration rate (eGFR <60 ml/min). This takes into account that patients can have significant reduction in eGFR whilst having normal plasma creatinine. Therefore the ability of the kidney to clear the plasma of creatinine will be assessed more accurately by the modification of diet in renal disease method (MDRD) [23].**

7. PLANNED TRIAL INTERVENTIONS

Patients that fulfil inclusion and exclusion criteria will be asked to give consent for the study at least a day before surgery and will be randomised into either of the two study groups on the day of surgery as follows:

1. ON-pump coronary artery bypass graft (CABG) surgery patients with GFR<60 ml/min without haemofiltration (control group)
2. ON-pump CABG surgery patients with GFR <60 ml/min undergoing haemofiltration (Experimental group)

7.1 CONTROL ARM

Patients will receive standard cardiopulmonary bypass without haemofiltration. Patients with preoperative fluid overload will be managed as per normal standard practice for kidney management of using diuretics with or without inotropes, dopexamine, and post-operative haemofiltration when needed.

7.2 EXPERIMENTAL ARM

Patients will be given a Zero-Balance Ultrafiltration Technique (Z-BUF) during cardiopulmonary bypass (CPB). The technique is used for all renal impaired patients that require active management on CPB and continues from the establishment of safe CPB to

just prior to termination of CBP. As fluid is removed from the circulation an equivalent amount of fluid, usually Accusol 35 is added to the circulation to replace it. Therefore a fluid exchange is occurring removing potentially harmful metabolites and pro-inflammatory markers. The overall fluid balance is maintained relatively constant as is the patient's haematocrit.

7.2.1 Z-BUF PROCEDURE

During CPB haemofiltration is a simple procedure where blood is drawn passively from the CPB circuit using the arterial pump pressure to drive the flow through the hemofilter. To prevent patient blood flow being compromised, the arterial pump rate will be increased to compensate for the blood flow through the haemofilter.

The hydrostatic pressure difference occurring across the haemofilter membrane termed the transmembrane pressure (TMP) provides the driving force for filtration. TMP is a function of the average pressure within the blood path minus the pressure on the effluent side. TMP can be altered by modifying these variables. In this study a high filtration rate will be achieved by using a high pressure source for the inlet to the filter and if necessary modification of the pressure at the outlet and/or on the effluent side. The haemofilter blood contact surface is 1.2 m² through Polysulfone (PS-Polypure) pre-set filter unit that is able to remove protein macromolecules to a molecular size of 30,000Da. A minimum exchange of approximately 6000 ml/hr which is a filtration rate of 100ml/min can be maintained. Fluid removed will be replaced with Accusol 35 a balanced salt crystalloid solution.

7.3 PILOT HEALTH CARE RESOURCE UTILISATION EVALUATION

The pilot study has two health economic objectives: a) to pilot test the data collection tools for quantifying resource use b) to determine the optimal sample size of an eventual randomised controlled trial using Value of Information analysis principles.

7.4 INCLUSION CRITERIA

Consenting men and women must be at least 18 years old, high-risk patients elective for on-pump coronary artery bypass graft surgery (CABG). They must also have

impaired renal function established preoperative by an estimated glomerular filtration rate (eGFR) <60 ml/min measured within 4 weeks before surgery.

7.5 EXCLUSION CRITERIA

Patients undergoing surgery on the great vessels (aortic surgery) or valve surgery, have significant impaired liver function (serum bilirubin > 60 or INR > 2 without anticoagulation), patients who are further down the line of renal failure (i.e. eGFR < 15 ml/min) or on-dialysis, have malignancy and those that are pregnant.

8. STUDY POPULATION AND RECRUITMENT STRATEGY

Patients from the routine waiting list for CABG operations will be pre-screened for inclusion/exclusion criteria and will be informed about the trial by the investigators during their initial visit to the hospital for investigations. Eligible patients will be asked to sign a written consent form by the consultant in receipt of the initial referral or research nurse at the time of their surgical outpatient visit. In-patients will be given at least 12-24 hours time to study the patient information and consent will be sought **on the day before the operation**. Patients will only enter the active phase after having provided informed written consent and are included in the trial register. Patients that drop out prior to randomisation after registration will be logged on to the CONSORT diagram but not included in the intention-to-treat analysis.

9. RANDOMISATION

Random block sizes of 2, 4, and 6 will ensure numerical balance between the two groups. Patients will be stratified at the design stage on the basis of diabetes mellitus and the level of eGFR (eGFR < 40 > 15 ml/min *versus* eGFR > 40 < 60 ml/min). The randomisation service will be available 09:00 – 17:00 (UK time). Once randomised, the patient will be enrolled into the study and data will contribute to the primary outcome.

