15. FOLLOW UP DATA COLLECTION

1. Follow-up will be during the in-hospital stay phase and at 6 weeks post-discharge follow-up visit.
2. All information will be collected in structured Case Record Forms (CRFs).
3. A Manual of Operation documents containing relevant procedural instructions and definitions will be produced.
4. Data will be entered into a secure password protected database.
5. Prospective monitoring of adverse and clinical events will start at randomisation and will continue until hospital discharge
6. Costs associated with each of the two pilot arms, postoperative renal replacement therapy, ICU stay and hospital ward stay, and medications will be estimated up until hospital discharge.

7. Prospective monitoring of serious adverse and clinical events will start at randomisation and will continue until hospital discharge.

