16. PLANNED ANALYSES

Intention to treat will be considered as the primary analysis. The clinical and economic impact of intraoperative haemofiltration versus no haemofiltration treatment will be examined. Analysis of the primary endpoint and other continuous data will be performed by using a 2-sided unpaired t-test or an equivalent non-parametric test. Categorical secondary outcome measures will be examined using a Chi-square test or Fisher's exact test as required. The potential cost differences per patient will be estimated with confidence intervals. Exploratory analysis will be undertaken using Bayesian Value of Information methods described by Tan and Smith [25] that balances the benefit of detecting a minimally significant difference with at least a given power against the costs of the patient sample size and/or the risk that the research poses to patients. The result of this analysis will provide guidance on the optimal sample size to use in a future RCT that would seek to evaluate the impact of haemofiltration on healthcare costs.

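### Randomisation is stratified by diabetes and eGFR, but the named two-group tests use neither the strata nor baseline eGFR, and the printed eGFR strata omit exactly 40 and exactly 15

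*Protocol*

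**What the plan says.** Protocol Section 9 stratifies: "Patients will be stratified at the design stage on the basis of diabetes mellitus and the level of eGFR". The two eGFR levels are printed as "eGFR < 40 > 15 ml/min *versus* eGFR > 40 < 60 ml/min". With diabetes yes or no this makes four strata. On blocking it says "Random block sizes of 2, 4, and 6 will ensure numerical balance between the two groups".

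Section 16 is the only place that names tests for the arm comparisons. For the primary endpoint and continuous outcomes: "Analysis of the primary endpoint and other continuous data will be performed by using a 2-sided unpaired t-test or an equivalent non-parametric test". For the rest: "Categorical secondary outcome measures will be examined using a Chi-square test", or Fisher's exact test. Neither sentence mentions the strata or a baseline value, and no other section brings them into an analysis. Confidence intervals are promised only for the cost difference per patient, with no method stated.

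Baseline eGFR exists for everyone, because Section 7.4 requires "eGFR) <60 ml/min measured within 4 weeks before surgery". Section 14 lists 6-week eGFR as a secondary outcome, and Section 15 provides the visit: "Follow-up will be during the in-hospital stay phase and at 6 weeks post-discharge follow-up visit". At the lower end of eligibility, Section 7.5 excludes "i.e. eGFR < 15 ml/min) or on-dialysis".

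**The concern.** Stratified blocking makes the arms alike on diabetes and eGFR level. If those factors predict outcome, the difference between arms varies less from trial to trial than simple randomisation would allow. An unpaired t-test does not know this. It counts the variation between strata as error, so its standard error is too large and its real error rate falls below the nominal 5%.

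For 6-week eGFR there is a second loss. The best single predictor is probably the patient's own preoperative eGFR, and two broad classes carry only part of that information. Section 4 states a hypothesis about progression of renal impairment, which is change from the starting value, yet the named test compares raw 6-week values. The pilot is meant to judge whether its outcome measures are suitable for the main trial, and an analysis that leaves in removable variance can make a usable outcome look too noisy.

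The boundary gap is a practical matter. A patient who falls in no stratum cannot be allocated as the protocol describes, and staff would have to choose a stratum on the day of surgery.

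**Working it through.** **1. The plan's own figure.** Section 13 gives 1112 patients for the main trial: 18% versus 12%, 80% power, two-sided 0.05. With pooled variance and no continuity correction, n per arm = [1.960·√(2·0.15·0.85) + 0.842·√(0.18·0.82 + 0.12·0.88)]² / 0.06² = (0.990 + 0.423)² / 0.0036, about 555, or 1110 in total. The figure reproduces to within 2 patients. It rests on an unadjusted comparison of two proportions and is not in dispute here.

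**2. 6-week eGFR.** The documents give no correlation between baseline and 6-week eGFR, so a range is assumed. Further assumptions: 35% diabetic; baseline eGFR normal with mean 47 and SD 10, cut to 15–60; diabetes itself not prognostic; no treatment effect. From the protocol: 60 patients, four strata, blocks of 2, 4 and 6. There were 6,000 simulated trials per correlation, so a true 5% rate is measured to about ±0.6 points (2·√(0.05·0.95/6000)).

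| Assumed correlation | Interval width, strata in model / unadjusted | Interval width, strata and baseline / unadjusted | √(1−ρ²) | Type I error of t-test | Type I error, strata and baseline |
|---|---|---|---|---|---|
| 0.3 | 0.97 | 0.96 | 0.95 | 4.6% | 5.4% |
| 0.5 | 0.92 | 0.87 | 0.87 | 4.1% | 5.6% |
| 0.7 | 0.83 | 0.71 | 0.71 | 2.2% | 5.1% |
| 0.8 | 0.77 | 0.59 | 0.60 | 1.3% | 4.5% |

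The simulated widths agree with the textbook ratio √(1−ρ²) to within 0.01.

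Part of the narrowing corrects an overstated standard error and part is real precision. At correlation 0.8 the t-test's standard error is about √(2/30) = 0.258 outcome SDs, while the estimate really varied with SD 0.209. Strata in the model barely change that spread (0.202); continuous baseline eGFR reduces it to 0.156.

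**3. Primary outcome (ICU stay over 3 days).** Section 16 groups this endpoint with continuous data, although Section 14 defines it as yes or no. That is a separate matter, and the size is worked here on the binary scale. Assume 35% diabetic and 25% with eGFR below 40. The unadjusted interval exceeds the stratified one by the factor 1/√(1−R²), where R² is between-stratum variance over total variance.

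- No risk difference between strata: R² = 0, excess 0%.
- Stratum risks 13%, 26%, 19%, 36%: R² = 0.033, √0.967 = 0.983, excess about 2%.
- Stratum risks 10%, 30%, 20%, 50%: R² = 0.092, √0.908 = 0.953, excess about 5%.

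At 30 per arm the half-width at the planning rates is 1.96·√[(0.1476 + 0.1056)/30] = 0.18, or 18 percentage points. Expected events are 30·0.18 + 30·0.12 = 5.4 + 3.6 = 9, about 2 per stratum.

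**4. The strata against eligibility.** Sections 7.4 and 7.5 together admit eGFR from 15 up to, but not including, 60. Section 9 covers values strictly between 15 and 40 and strictly between 40 and 60. Eligible values without a stratum are exactly 40 and exactly 15. If eGFR is reported in whole numbers spread evenly over 15 to 59 (an assumption), there are 45 values, and 60/45 = 1.3 of 60 patients would be expected at 40. An even spread probably overstates how often 15 occurs.

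**The case against.** The best case for the plan is that little harm follows. The loss is on the conservative side. The stated objectives are recruitment and suitability of outcomes, not a test of efficacy, and the inputs to the 1112 calculation are crude event rates, which an unadjusted analysis reports directly. Covariate adjustment is commonly set out in a SAP, and Section 16 does not forbid it. All of this limits the importance of the point. It does not remove it, because Section 16 does more than stay silent: it names the tests, and a SAP that adjusted would have to go beyond them.

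The gain for 6-week eGFR also rests wholly on assumed correlations. Enrolment restricts baseline eGFR, which tends to lower a correlation, and at 0.3 the gain is only about 4% of interval width. That stands, and it is why a range is given.

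Several stronger readings are tempting but not supported:

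- *That the plan's confidence intervals are too wide.* Intervals are promised only for cost differences, by a method not stated. The point concerns the named tests and their standard errors.
- *That every planned comparison is unadjusted.* Section 16 also plans a Value of Information analysis and Section 16.2 subgroup analyses; neither is described as a two-group test.
- *That the loss is large for all outcomes.* If strata explained 20–30% of variance, a t-test at nominal 5% would run at about 2.8–2.3% in this design. Nothing in the documents supports that share, and for the primary outcome even the widest spread of risks tried above gives 9%.
- *That adjustment at correlation 0.8 is worth 60/(1−0.64) = 167 patients.* Stratification has already secured part of that gain. On the simulated spread of the estimates it is 60·(0.209/0.156)², about 108.

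**Conclusion.** The point holds in a limited form. Every two-group test that Section 16 names ignores the randomisation strata, and 6-week eGFR is to be compared without its baseline. The result is overstated standard errors and conservative tests where strata or baseline are prognostic, with no bias and no inflation of type I error.

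The consequence is material only for 6-week eGFR: an interval 0.96 to 0.59 as wide after adjustment, for assumed correlations of 0.3 to 0.8. For the primary outcome it is about 0 to 5%, small beside a half-width of 18 points.

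The gap in the eGFR strata depends on no statistical assumption. It follows from the printed inequalities and the eligibility limits, would probably touch one or two patients at most, and cannot be left to an analysis plan because allocation depends on it. Overall this is an improvement that should be made, not a flaw that invalidates the pilot.

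**What to change.** In Section 16:

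- Analyse 6-week eGFR by ANCOVA on continuous baseline eGFR plus diabetes.
- Analyse EQ-5D at 6 weeks with its admission value (collected under Section 14) plus the stratification factors.
- Analyse other continuous outcomes by a linear model with the stratification factors.
- For binary outcomes, keep any stratified analysis light, for example a Mantel-Haenszel risk difference reported beside the crude rates. With about 9 primary events expected, nothing heavier is workable, and the crude rates are still needed for the main-trial sample size.

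In Section 9, make the eGFR strata contiguous and covering the range that Sections 7.4 and 7.5 admit, for example 15 to <40 and 40 to <60, and set up the randomisation service to match before the first allocation.

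The cost is a wording amendment. All the variables are known before randomisation, so no new data, visits or patients are needed. If a SAP already specifies adjustment, Section 16 need only be brought into line with it.

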10. PROTECTING AGAINST OTHER SOURCES OF BIAS

It is very difficult to disguise the evidence of intraoperative haemofiltration during cardiopulmonary bypass. Although it is relatively easy to put up a haemofilter onto the pump

and prime it to look as if it is being run in the non-haemofiltration group there is other evidence such as the 5 L bags of “Accusol 35” that need to be hanging up and vac sacs full of waste solution that cannot be disguised. The surgeon may not ‘know’ which arm a patient is randomised to, but it would be nearly impossible to blind them from noticing the presence of vac sacs full of waste solution which is indicative of the haemofiltration procedure. Hence, only the patients are likely to be blinded as to whether zero-balance filtration has been applied. Discharge from ICU is based on Nurse Discharge Guidelines which are independent of ITU physicians and follows a scoring system termed “Modified Early Warning Score - MEWS” ranging from 0-3 days. Nurses discharge patients from ICU when the MEWS is <2.0 and that only consultant cardiac surgeons/intensivists are authorised to discharge a patient out of ITU when the total MEWS is >3.0. All ICU staff will be blinded as to whether or not the patient received intraoperative haemofiltration to eliminate bias.

Incidences such as infection, antibiotic usage, re-operation or re-opening of chest in ICU, postoperative anaemia, thrombocytopenia, hypoalbuminemia, post-operative bleeding and post-operative pulmonary complications which are potential confounding factors that determine ICU stay will be documented.

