14. STUDY OUTCOMES

Proposed Outcome Measures: These will be evaluated for suitability and reliability for the main trial - Our chosen primary outcome and secondary outcome measures will be monitored to ensure they are suitable and reliably informative of the impact of intraoperative haemofiltration. There is an element of concern that the outcomes could be confounded by crossovers between the experimental groups, in response to protocol deviation by clinicians. All protocol deviations will be documented in the database. The primary analysis will be completed on an intention to treat basis but separate information will be provided on the incidence and rate of protocol deviation and crossover. We will also report a range of other outcomes including key measures of resource utilisation and kidney function at 6 weeks follow-up to establish whether these may be suitable for the main trial. The outcome measures to be evaluated are:

PRIMARY OUTCOMES

Incidents of ICU stay >3 days for patients with renal impairment identified as an estimated glomerular filtration (eGFR) <60 ml/min.

SECONDARY OUTCOMES

CLINICAL OUTCOMES

- Composite of perioperative incidences: Bleeding, sepsis, death, arrhythmias, stroke, and myocardial infarction
- Need for postoperative continuous veno-venous haemofiltration (CVVH) in the ICU - Indications for requirement of postoperative continuous veno-venous haemofiltration must adhere to our **surgical guidelines**.
- Mechanical ventilation time
- Hospital stay
- eGFR at 6 weeks follow-up

SECONDARY ECONOMIC OUTCOMES: Resource utilisation and key costs indicators associated with each of the two pilot arms specifically ICU stay and hospital stay, postoperative renal replacement therapy, mechanical ventilation, medications, will be estimated up until hospital discharge. Participants will be required to complete health-related quality of life questionnaire EQ-5D at hospital admission before surgery and at the 6 weeks follow-up hospital visits.

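### Section 10 says blinding ICU staff eliminates bias, yet permits a surgeon who may know the allocation to authorise the ICU discharge that sets the primary outcome

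*Protocol*

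**What the plan says.** Section 14 defines the primary outcome as "Incidents of ICU stay >3 days for patients with renal impairment identified as an estimated glomerular filtration (eGFR) <60 ml/min". Section 6 describes the design as "Single centre, randomised open-label clinical trial".

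Section 10 then makes these statements about blinding and ICU discharge:

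- Of the surgeon it says that "it would be nearly impossible to blind them from noticing the presence of vac sacs full of waste solution".
- It concludes: "Hence, only the patients are likely to be blinded as to whether zero-balance filtration has been applied".
- It describes the basis of discharge: "Discharge from ICU is based on Nurse Discharge Guidelines which are independent of ITU physicians". Nurses discharge when the MEWS is below 2.0.
- Above a total MEWS of 3.0, "only consultant cardiac surgeons/intensivists are authorised to discharge a patient out of ITU when the total MEWS is >3.0".
- It closes: "All ICU staff will be blinded as to whether or not the patient received intraoperative haemofiltration to eliminate bias".

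**The concern.** In an unblinded surgical trial, an outcome that depends on when somebody releases the patient is protected only if that person does not know the allocation, or follows a rule that leaves no discretion. Section 10 claims the first kind of protection for ICU staff. For most discharges it appears to rely on the second, through the nurse MEWS rule. The consultant route above MEWS 3.0 has neither: it is a matter of judgement, and one of the two groups named for it includes the people the section has just said will probably know.

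A preference for the technique is plausible at this centre. Section 7.2 describes it as in use for renally impaired patients who need active management on bypass, and section 16.1 calls the procedures standard.

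The pilot's own aims are at stake. Section 4 lists the suitability and reliability of the outcome measures as an objective, and section 13 says the pilot data will be used to size the main trial. If the protocol assumes that discharge bias has been eliminated, and does not record who decided, the pilot cannot show whether this outcome is reliable.

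**Working it through.** **1. Can the statements in section 10 all stand?** The answer turns on whether the closing phrase about ICU staff includes the consultant surgeons who may authorise discharge.

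| Reading of ICU staff | Consequence |
|---|---|
| Includes those surgeons | The blinding claim contradicts the concession that the surgeon will notice the waste sacs |
| Excludes those surgeons | The sentences are consistent, but the blinding does not cover a named decision-maker for the primary outcome |

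On either reading, the claim that bias is eliminated is not supported. Two further tensions need reconciling. Discharge is said to be independent of ITU physicians, yet intensivists are named as authorising it. Patients are said to be the only ones likely to be blinded, yet all ICU staff are then said to be blinded.

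**2. Which discharges are exposed?**

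| MEWS | Who may discharge, per section 10 | Exposed to knowledge of allocation? |
|---|---|---|
| Below 2.0 | Nurses, by rule | Only if the nurses' blinding fails; how allocation is hidden from ICU is not described |
| 2.0 to 3.0 | Not stated | Cannot be judged |
| Above 3.0 | Consultant cardiac surgeon or intensivist | Possible, if the authorising person was in theatre |

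No other section limits the decision to someone who was not in theatre, or provides blinded assessment of the primary outcome.

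**3. Scale.** Inputs from section 13: 18% versus 12%, 80% power, two-sided alpha 0.05, 1112 patients in the main trial, 60 in the pilot. Equal allocation is inferred from the aim of numerical balance in section 9, giving about 30 per arm in the pilot and 556 in the main trial.

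The plan's figure first, with pooled variance and mean rate 0.15:

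n per arm = [1.96 × √(2 × 0.15 × 0.85) + 0.8416 × √(0.18 × 0.82 + 0.12 × 0.88)]² / 0.06² = 555, or 1110 in total. This agrees closely with 1112 and is not in dispute.

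The planned effect in patients:

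- Pilot: 30 × 0.18 = 5.4 against 30 × 0.12 = 3.6, a gap of 1.8. One patient is 1/30 = 3.3 points.
- Main trial: 556 × 0.06 = 33.4.

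The pilot gap is small because the pilot is small. It would be the same for any kind of misclassification, so it does not measure this defect.

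**4. Illustration for a main trial with the same discharge arrangement.** Assume no true effect, and that a fraction f of the long stays in the experimental arm is moved to 3 days or less because the allocation is known. The apparent rate is 0.18 × (1 − f). The chance of a significant result favouring haemofiltration at 556 per arm is Φ[(d − 1.96 × SE₀)/SE₁], where d = 0.18 × f, SE₀ is the pooled standard error and SE₁ the unpooled one.

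| f (assumed) | Apparent rate | Chance of a false significant benefit |
|---|---|---|
| 5% | 17.1% | 6% |
| 10% | 16.2% | 12% |
| 20% | 14.4% | 37% |
| 33% | 12.0% | 80% |

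The nominal chance in that direction is 2.5%. The value f = 1/3 is 0.06/0.18, the whole planned effect. The protocol gives neither f nor the share of discharges made above MEWS 3.0.

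**The case against.** The strongest reply is that the gap is narrow. The default route is a nurse rule, the consultant clause only restricts who may release a patient still scoring high, an intensivist may be the one who decides, and the trial declares itself open-label and is a feasibility pilot. The remark that only patients are likely to be blinded closes a discussion of what is visible in theatre, and may be meant for those present there. All of this stands, and it lowers the severity.

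A reader might also infer stronger points that the protocol does not support:

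- *That all discharge decision-makers are claimed to be blinded.* The text says ICU staff, which need not include a cardiac surgeon.
- *That an unblinded surgeon does decide for these patients.* This is permitted, not certain. The authorising surgeon need not be the one who operated, and may be replaced by an intensivist.
- *That surgeons could hold control patients longer.* Nurses discharge below 2.0 and no power to override them is given. Release while the score is still above 3.0 is the clearer route.
- *That long stays are concentrated above MEWS 3.0.* This is plausible, but no figure supports it. A long-stay patient may wait until the score falls and leave by the nurse route.
- *That the pilot will carry a biased outcome into the main trial.* The pilot exists partly to check the outcome.

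What the reply does not answer is that section 10 states that bias is eliminated, and its own text leaves a route open.

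**Conclusion.** The concern holds in a limited form. The protection claimed in section 10 is stronger than the arrangement it describes: for some patients, someone who may know the allocation can decide whether the stay exceeds 3 days. This follows from the text alone and does not depend on any assumed rate.

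The size of any resulting bias cannot be derived. The illustrative error rates rest on assumed fractions, equal allocation, and a main trial that keeps the same discharge arrangement. They show only that a main trial of the planned size would be sensitive to moderate shifts.

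Severity is moderate. The pilot is open-label and not sized for efficacy, but it is meant to test whether this outcome is reliable, and as written it would not collect what is needed to judge that.

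**What to change.** 1. In section 10, reconcile the blinding and discharge statements, including the unassigned range from 2.0 to 3.0 and the description of the score as running from 0 to 3 days. Replace the closing sentence with a plain statement of who is and is not blinded. Which discharge rule is right is for the clinical team.
2. Record on the CRF the role of the person who authorised ICU discharge, whether that person was in theatre for the operation, and the MEWS at discharge.
3. Beside actual ICU stay, report a supportive version of the primary outcome timed from when the nurse criterion (MEWS below 2.0) was first met. This needs the time of that score on the CRF. A patient who leaves ICU above 3.0 may not yet have met the criterion. If no later scores are available, show the result with such patients counted each way. This version still relies on nurse scoring, so the statement in item 1 should say how allocation is kept from the nurses.

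The cost is protocol wording, a few CRF fields and one more analysis. No change to who may discharge, or to the information handed over to ICU, is proposed. In return, the pilot can report how often discretionary discharge set the outcome, which the main trial will need to know.
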